8.3 PMEWS

PMEWS uses six physiological parameters and patient parameters to calculate a score from zero to 19. The score is calculated by taking the score in the table below dependent on each of the six physiological parameters then adding points for two patient parameters after if they are positive.

Physiological:

Score	3	2	1	0	1	2	3
Respiratory Rate	≤8			9-18	19-25	26-29	≥30
SaO ₂	<89	90-93	94-96	>96			
Pulse Rate	≤40	41-50		51-100	101-110	111-129	≥130
Systolic BP	≤70	71-90	90-100	>100			
Temperature		≤35.0	35.1-36.0	36.1-37.9	38-38.9	≥39	
Neuro				Alert	Confused Agitated*	Voice	Pain Uncon

* confused/agitated will be defined based on GCS-V<4 or GCS total<15, or if confusion is ticked as a presenting feature

Patient:

- 1. Add 1 point if age>65
- 2. Add 1 point if either:
 - a. Patient lives alone / no fixed abode or
 - b. has a co-morbidity (respiratory, cardiac, renal, immunosuppressed, diabetes)
 - c. performance status is more than two suggesting limited activity can self-care, limited activity limited self-care, or bed/chair bound no self-care.

Missing data: If data is missing one or two variables then the normal score (zero) should be assumed. If more than three variables are missing the patient should be excluded. These rules effectively classify

missing data as normal. Low rates of missing data are expected for the physiological parameters and age. The remaining parameters only account for one point and therefore would be within the range of using the patient data. Sensitivity analysis will be considered if physiological variables have missing rates > 5%. If AVPU is missing and GCS is recorded, impute the following AVPU scores using GCS: 0 if GCS=15, 1 if GCS=12-14; 2 if GCS=9-11 and 3 if GCS<9.

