6.2 Existing triage tools

We will evaluate the following existing triage methods:

- CURB-65 [7]
- PMEWS [8]
- The Swine Flu Hospital Pathway [9]
- NEWS2 [10]

- The WHO decision-making algorithm for hospitalisation with pneumonia [11]
- POPS [12]
- COAST [13]

The triage tools will be retrospectively applied to the data by the study statisticians. CURB-65 and PMEWS will be evaluated in adults only, NEWS2 will be evaluated in adults excluding pregnant women, POPS will be evaluated in children only. Details of scoring and handling missing data for the triage tools are given in sections 8.2 to 8.5. Existing triage tools will be assessed by plotting the ROC curve and calculating the area under the ROC curve (c-statistic) for discriminating between cases with and without adverse outcome. Sensitivity, specificity, positive predictive value and negative predictive value at key decision making thresholds will be calculated and presented:

Tool	Threshold
CURB-65	0-1 versus 2-5
PMEWS	0-2 versus 3+
The Swine Flu Hospital Pathway	0 versus 1+
NEWS2	0-4 versus 5-20, 0-4 versus 50-20 or scoring at least
	3 in one category
WHO	0 versus 1
POPS	0-4 versus 5+
COAST	0-2 versus 3+

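### The PMEWS scoring rules in SAP section 8.3 give no score to SaO2 89%, two scores to a systolic BP of 90 mmHg, and no explicit rule for exactly three missing variables

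*SAP*

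**What the plan says.** Section 6.2 lists PMEWS among the existing tools, to be evaluated in adults by AUROC and by sensitivity, specificity and predictive values at 0-2 versus 3+. On who computes the scores it says "The triage tools will be retrospectively applied to the data by the study statisticians". Section 8.3 is therefore the coding specification.

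Section 8.3 states that "PMEWS uses six physiological parameters and patient parameters to calculate a score from zero to 19". Two rows of its table matter here, each running from 3 points down to 0:

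- SaO2: "<89 90-93 94-96 >96"
- Systolic BP: "≤70 71-90 90-100 >100"

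On missing items it says "If data is missing one or two variables then the normal score (zero) should be assumed", and then "If more than three variables are missing the patient should be excluded". It adds that these rules amount to classifying "missing data as normal. Low rates of missing data are expected for the physiological parameters and age".

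The threshold table in section 6.2 and the summary table in section 8.9 deal only in total scores. Neither settles an individual item.

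**The concern.** A scoring table that will be turned into code needs exactly one score for every value that can be recorded. This one fails at one SaO2 value and one systolic BP value, and the missing-data rule skips one count. Two statisticians who followed section 8.3 faithfully could give the same adult different PMEWS totals, or differ on whether that adult is scored at all.

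The cut-off is low (3 points) and the SaO2 item alone can contribute up to 3, so a mis-scored saturation can move a patient across it. What is at stake is the accuracy reported for PMEWS. Through that, section 6.5 could also be touched, because the existing tool with the best AUROC in the development cohort becomes the comparator for the new tools.

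**Working it through.** **Reading of the table.** The maximum points per row are respiratory rate 3, SaO2 3, pulse 3, systolic BP 3, temperature 2 and neuro 3. Sum: 3 + 3 + 3 + 3 + 2 + 3 = 17. Adding the 2 patient points gives 19, which is the maximum stated in section 8.3. The table has been read as intended.

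**Coverage check.** Each numeric row was tested for exactly one matching band, in whole numbers (0.1 degree steps for temperature). That SaO2 and BP are recorded as whole numbers is an assumption.

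| Row | Result |
|---|---|
| Respiratory rate | every value has one score |
| SaO2 | 89 has no score |
| Pulse | every value has one score |
| Systolic BP | 90 has two scores, 2 and 1 |
| Temperature | every value has one score |

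**Missing-count check** (eight items): 1-2 missing, score as zero; 4-8 missing, exclude; 3 missing, no explicit rule.

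**Effect of SaO2 89% on the class (0-2 low, 3+ high).** The SAP gives no score, so three codings are compared: 0 (unmatched treated as normal), 2 (joined to 90-93) and 3 (joined to <89).

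| Points from other items | coded 0 | coded 2 | coded 3 |
|---|---|---|---|
| 0 | low | low | high |
| 1 | low | high | high |
| 2 | low | high | high |
| 3 or more | high | high | high |

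Example: a respiratory rate of 20 scores 1, and all else is normal. At SaO2 88 the total is 1 + 3 = 4, and at SaO2 91 it is 1 + 2 = 3. At SaO2 89 it is 1, 3 or 4, depending on the coding.

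**Effect of systolic BP 90.** It is coded 1 or 2.

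| Points from other items | coded 1 | coded 2 |
|---|---|---|
| 0 | 1, low | 2, low |
| 1 | 2, low | 3, high |
| 2 or more | 3+, high | 4+, high |

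The class changes only when the other points total exactly 1.

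**Comparison within the SAP.** The NEWS2 table in section 8.5 has no gap or overlap in the same two rows (SaO2 ≤91, 92-93, 94-95, ≥96; systolic BP ≤90, 91-100, 101-110, 111-219, ≥220). The completeness rules for the other tools (sections 8.2 and 8.4 to 8.8) turn on whether at least three items are available, which leaves no count uncovered. PDF damage is unlikely, because ≤ survives in other cells of the PMEWS table and 90 is printed in both BP cells.

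**The case against.** The strongest reply is that these are transcription slips at single boundary values in one of seven retrospectively applied tools, and that the cited PMEWS source would settle them. Four parts of that reply stand.

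- A reader might infer that 89% drops to 0 as normal. The SAP does not say so. Zero is assigned to missing variables, and a recorded 89% is not missing; the table gives 0 only above 96. Coding to 0 is a plausible accident in code, not a stated rule.
- A reader might infer that all three faults cause hypoxic adults to be scored as low risk. Only the SaO2 gap could do that. The BP overlap moves one point at most, and the three-missing gap has nothing to do with hypoxia in particular.
- The missing-data text leans towards an answer. Only more than three missing leads to exclusion, and the section describes its rules as treating missing as normal. It also expects little missing physiology.
- Many adults reading 89% would have 3 or more points from respiratory rate, pulse, temperature, age or comorbidity. Their class is the same under any coding.

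What does not stand is that nothing needs correcting. No other section assigns 89%, chooses a score for 90 mmHg or states the three-missing case, and the printed table is what will be programmed.

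**Conclusion.** The scoring specification is wrong as written in three places, and it should be corrected before PMEWS is computed. The gap, the overlap and the unstated count are there whatever is assumed. Their effect on results is narrower:

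- SaO2 of exactly 89%: with 1 or 2 other points, coding it 0 gives low risk where either neighbouring band gives high. With no other points, the class depends on which band is intended. With 3 or more, nothing changes.
- Systolic BP of exactly 90 mmHg: the class changes only with exactly 1 other point.
- Exactly three missing variables: the open question is whether the patient is scored or excluded, which changes the denominator.

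The number of adults affected is not in the SAP and is probably small. A reader might infer a definite loss of sensitivity. If 1-3% of the 200 planned events had SaO2 of exactly 89%, that would be 2-6 events, or 1-3 percentage points. But that share is an assumption, and the figure is a ceiling: it needs every such event to be coded 0 and to have at most 2 other points. The direction of any change in AUROC is not established either, since patients without events would lose points too.

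A different comparator in section 6.5 is possible but not shown. It would need the cohort to be split (at least 400 events) and PMEWS to be close to the best AUROC. Because scoring is retrospective, patient care is not affected. The harm is to the correctness and reproducibility of the PMEWS AUROC, sensitivity and specificity.

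**What to change.** Reconcile the SaO2 and systolic BP rows of the section 8.3 table with the source chart that the SAP cites, so that every integer value has exactly one score. The SAP alone does not show which band 89% or 90 mmHg belongs to, so none is proposed here.

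Replace the two missing-data sentences with one rule that covers every count, including exactly three. The existing text points to scoring those items as normal, since only more than three leads to exclusion, but this should be stated. Say also that a recorded value matching no band is an error to be resolved and not a missing value.

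Before analysis, run the coded score over a test file with every integer value of each item (0.1 degree steps for temperature) and every count of missing items.

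The cost is two table rows, one or two sentences and a short code check. No new data are needed.

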8.4 Swine Flu Hospital Pathway

The Swine Flu Hospital Pathway consists of seven criteria, if any one of the criteria meet the threshold they should be admitted. The criteria thresholds are different for adults and children, these are in the table below.

Criteria	Critoria	Adult Threshold	Child Threshold
Label	Cinteria	Addit Threshold	
A	Severe respiratory distress	Severe breathlessness (severe	Lower chest wall indrawing, sternal
		respiratory distress ticked on	recession, grunting or noise breathing
		form)	when calm (severe respiratory distress
			ticked on form)
В	Respiratory rate	Over 30 breaths per minute	50+ breaths per minute if under 1, 40+
			breaths per minute if 1+ years
С	Oxygen saturation	≤92% on pulse oximetry,	≤92% on pulse oximetry, breathing air
		breathing air or on oxygen	or on oxygen
D	Respiratory exhaustion	New abnormal breathing pattern	Exhaustion or apnoeic episode (20+
		(respiratory exhaustion ticked on	second pause in breathing) (respiratory
		form)	exhaustion ticked on form)
E	Dehydration or shock ^a	Systolic BP <90 mmHg and /or	Sternal capillary refill time >2 seconds,
		diastolic BP <60 mmHg.	reduced skin turgor, sunken eyes or
		Sternal capillary refill time >2	fontanelle
		seconds, reduced skin turgor	
F	Altered conscious level ^b	New confusion, striking agitation	Strikingly agitated or irritable, seizures
		or seizures	or floppy infant
G	Other clinical concern ^c	Another clinical concern	Another clinical concern

a) dehydration or shock will be defined in adults if they are labelled as having severe dehydration, or
Systolic BP <90 mmHg and /or diastolic BP <60 mmHg, or central capillary refill is categorised as abnormal.
In children it will be defined as having severe dehydration or central capillary refill categorised as abnormal.
B) Altered conscious will be positive if GCS is less than 15 or AVPU is anything other than A. C) Other clinical concern is not recorded in the data, two scores will be calculated, one where point G is ignored and the Swine Flu hospital pathway is calculated based on the first 6 items, and another where clinical concern is considered positive if NEWS2>4 or any parameter in NEWS2 is given a score of 3.

Missing data: As the measure only requires one score then missing data will be classified as normal. Low rates of missing data are expected for the physiological parameters however it will not be possible to determine whether failure to tick the relevant boxes represented missing data or not. The measure will not be calculated if fewer than three of the parameters are complete.

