6.3 Presenting clinical characteristics and routine tests

For all characteristics (candidate predictors) we will present the odds ratio, p-value and 95% confidence interval (CI) from a univariable analysis. For binary characteristics we will also present the distribution of adverse outcomes in each category. If a continuous characteristic has pre-specified cut-off points the distribution of adverse outcomes will be presented for each category.

The following clinical characteristics and routine tests will be evaluated.

Continuous Characteristic	Cut offs	Adults	Children	Initial assessment model	Full model
Age	None	\checkmark	\checkmark	\checkmark	\checkmark

Symptom duration		✓	~	✓	✓
Number of current		1	1	√	√
medications		·		·	·
Urea		√	✓		✓
Creatinine		√	~		✓
Respiratory rate	0= 12-20 or missing 1= 9-11	1			
	2= 21-24 3= <9 or >24	·	v	· ·	· ·
Pulse rate	0= 51-90 or missing 1= 41-50 or				
	91-100 2= 111-130 3= <41 or	\checkmark	~	~	\checkmark
	>130				
Temperature	0= 36.1-38.0 or missing 1= 35.1-				
	36.0 or 38.1-39.0 2= >39.0 3=	✓	✓	~	✓
	<35.1				
Systolic Blood	0= 111-219 or missing 1=101-				/
Pressure	110 2= 91-100 3= <91 or >219	v	v	v	v
SaO ₂	0= >95 or missing 1= 94-95 2=				
	92-93 3= <93 (add two points	✓	✓	✓	\checkmark
	for FiO ₂ >21%)				
SaO ₂ /FiO ₂ ratio		✓	✓	√	✓
GCS Total ^a	1= Severe (<8) 2= Moderate (9-				/
	12) 3= Mild (13-15)	v	v	v	v
Na	1= Low (<136) 2=Normal (136-				
	142) 3 = High (>142)	v	v		v
К	1= Low (<3.5) 2=Normal (3.5-				
	5.0) 3 = High (>5.0)	v	v		v
Hb	1= Low (<130 males, <115				
	females) 2=Normal (130-180				/
	males, 115-165 females) 3 =	v	v		v
	High (>180 males, 165 females)				
Platelets	1= Low (<150) 2=Normal (150-				/
	400) 3 = High (>400)	v	v		v
WCC	1= Low (<4) 2=Normal (4-11) 3	1	1		
	= High (>11)	V	V		V
Neutrophils	1= Low (<2.0) 2=Normal (2.0-				
	7.5) 3 = High (>7.5)	V	V		V
Lymphocytes	1= Low (<1.5) 2=Normal (1.5-				
	4.5) 3 = High (>4.5)	~	×		√
Lactate		✓	✓		~

C-Reactive	~	~	~
D-dimer	~	~	~
Troponin	~	~	~

a) Both GCE and AVPU will be analysed in univariable analysis, however in multivariable analysis AVPU will be used and missing AVPU data will be imputed using GCE scores (see section 7.1.2 for the imputation rules).

Binary				Initial	
Characteristic	Levels	Adults	Children	assessment	Full model
enaracteristic				model	
Sex	Male/Female	~	~	~	\checkmark
Presenting features	Presence/Absence per feature				
(Shortness of breath,					
cough, fever, sore					
throat, headache,		1	1	 	1

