8.5 NEWS2

The NEWS2 has seven parameters which are scores from zero to three providing an overall score between zero and 20. The scores for each parameter can be found in the table below.

Score	3	2	1	0	1	2	3
Respiratory Rate	≤8		9-11	12-20		21-24	≥25
SaO₂	≤91	92-93	94-95	≥96			
Pulse Rate	≤40		41-50	51-90	91-110	111-130	≥131
Systolic BP	≤90	91-100	101-110	111-219			≥220
Temperature	≤35.0		35.1-36.0	36.1-38.0	38.1-39.0	≥39.1	
Neuro				Alert			Confusion, Voice, Pain, Unresponsive
Air or Oxygen		Oxygen (based on FiO ₂ >21%, or FiO ₂ >0 L/min)		Air			

Missing data: Any missing data will be imputed with the value zero, therefore classifying missing as normal. Low rates of missing data are expected for the physiological parameters. Sensitivity analysis will be considered if physiological variables have missing rates > 5%. The score will not be calculated if fewer than three of the parameters are available. The scale for patients with confirmed hypercapnic respiratory failure will not be used. For ROC analysis the raw score outlined above will be used. To calculate sensitivity and specificity at key cut-offs high risk will be defined as scoring at least 5, or scoring 3 points in any one of the above categories.

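### The second Swine Flu Hospital Pathway score sets criterion G from adult NEWS2 bands with no age limit, so under-5s with a recorded normal respiratory rate are counted as positive

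*SAP*

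**What the plan says.** Section 8.4 says of the pathway that "The criteria thresholds are different for adults and children, these are in the table below", and that "if any one of the criteria meet the threshold they should be admitted". Child criterion B (respiratory rate) is met at 50 or more under 1 year and at 40 or more from 1 year. Footnote a) defines dehydration or shock separately for adults and children.

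Criterion G, other clinical concern, is not in the data. Footnote c) therefore sets up two scores: "one where point G is ignored and the Swine Flu hospital pathway is calculated based on the first 6 items", and a second in which "clinical concern is considered positive if NEWS2>4 or any parameter in NEWS2 is given a score of 3". Footnote c) makes no adult/child split. Neither score is named as primary, and the summary table in 8.9 lists the pathway with seven items.

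Section 6.2 states that "NEWS2 will be evaluated in adults excluding pregnant women". It sets no age limit on the pathway, whose threshold is 0 versus 1+. Section 8.5 gives one set of NEWS2 bands.

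In section 6.3 the respiratory-rate bands begin "0= 12-20 or missing 1= 9-11" and end with category 3 for below 9 or above 24. Pulse category 3 is below 41 or above 130. Both rows are ticked for adults and for children, with no paediatric alternative.

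**The concern.** Followed as written, footnote c) has the programmer score NEWS2 in children. Normal respiratory and pulse rates are higher in young children than the adult bands allow, and the SAP's own POPS chart says so. A single parameter scoring 3 is enough for G, and G alone is enough for a positive pathway. A healthy respiratory rate would then mark a young child as high risk.

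This also overrides the child rules of the pathway itself. A rate of 25-49 under 1 year, or 25-39 from 1 year, is negative on criterion B but positive through G. Footnote a) leaves blood pressure out of the child definition of shock, yet a NEWS2 systolic pressure of 90 or less scores 3 and brings it back.

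Children are a primary analysis set (5.2), and this pathway is one of the few existing tools compared in them. At stake are the sensitivity, specificity and predictive values reported in children for the second score.

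**Working it through.** The SAP states no specificity or child age mix for this point, so there is no figure to reproduce. The check maps one SAP table onto another.

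**Inputs.** NEWS2 bands from 8.5. Respiratory rate: 12-20 scores 0, 21-24 scores 2, 25 or more scores 3. Pulse: 131 or more scores 3. Normal ranges are the score-0 column of the POPS chart in 8.7. Each whole-number value in a normal range is counted; these are shares of values, not of patients.

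| Age | POPS-normal respiratory rate | Values scoring 3 | POPS-normal pulse | Values scoring 3 |
|---|---|---|---|---|
| 0-1 | 30-40 | 11 of 11 | 110-160 | 30 of 51 |
| 1-2 | 25-35 | 11 of 11 | 100-150 | 20 of 51 |
| 2-5 | 25-30 | 6 of 6 | 95-140 | 10 of 46 |
| 5-12 | 20-25 | 1 of 6 (25 only) | 80-120 | 0 of 41 |
| 13-16 | 15-20 | 0 of 6 | 60-100 | 0 of 41 |

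In the three youngest bands every normal respiratory rate makes G positive, and so the pathway positive. Specificity among event-free under-5s with a recorded POPS-normal rate is therefore 0%.

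**Without G.** The highest POPS-normal rates are 40 (0-1), 35 (1-2) and 30 (2-5). Criterion B needs 50 under 1 year and 40 from 1 year, so none of these meets it. The six-item score does not have the problem.

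**All children.** This needs three quantities that the SAP does not give, so they are assumptions, treated as independent:
- S0: specificity of the six-item score
- u: share of event-free children who are under 5
- r: share of those with a recorded rate of 25 or more

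Counting only the respiratory-rate route in under-5s, specificity of the second score = S0 × (1 − u × r). With S0 = 0.80:

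| u | r = 0.6 | r = 0.8 | r = 1.0 |
|---|---|---|---|
| 0.25 | 0.68 | 0.64 | 0.60 |
| 0.50 | 0.56 | 0.48 | 0.40 |
| 0.75 | 0.44 | 0.32 | 0.20 |

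For example, 0.80 × (1 − 0.50 × 0.8) = 0.48. For S0 from 0.60 to 0.95 and the same u and r, the range is 0.60 × (1 − 0.75 × 1.0) = 0.15 to 0.95 × (1 − 0.25 × 0.6) = 0.81.

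**Section 6.3.** Category 3 (above 24) holds every POPS-normal respiratory rate in the three youngest bands. Category 0 holds 12-20 and missing, but POPS scores every rate in 12-20 as 1 or 2 at those ages. For these children the ordering is partly reversed, and a missing rate joins values that POPS calls abnormal. Pulse above 130 captures part of the normal range, in the shares tabulated above.

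**The case against.** The strongest reply is that section 6.2 already confines NEWS2 to non-pregnant adults, so no NEWS2 score exists for children and footnote c) can operate only in adults. That reading is possible, but the SAP does not state it. Section 6.2 limits where NEWS2 is evaluated as a tool in its own right; footnote c) borrows it to build a different tool that is scored in children, and it omits the age split that footnote a) makes. A programmer could follow the text either way.

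Other parts of the reply stand:
- Only one of two pathway scores is affected, and the six-item score is planned anyway.
- NEWS2 scores a missing rate as normal, so a child without a recorded rate is not made positive by this route.
- A reader might infer that child specificity collapses generally. The documents do not support that: by respiratory rate the effect is near nil from age 5, and the age mix is unknown.
- A reader might also infer that the AUROC falls to chance level. That requires a binary any-positive score. The threshold of 0 versus 1+ (against 0 versus 1 for the WHO tool) may mean a count of criteria, and the summary table gives no score range. With a count, a G that is positive in every child of a group adds 1 to each and leaves the ranking within that group unchanged.
- The 6.3 cut-offs classify nobody as high risk and have no specificity of their own. Models start with continuous predictors, child models are conditional on enough events, and clinical PMG members review the cut-offs. What remains certain is the child table of outcomes by category, which 6.3 says will be presented; the subsection on converting the model into a triage tool also expects these cut-offs to be used.

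**Conclusion.** The point holds for the second pathway score in young children. As written, footnote c) makes every under-5 with a recorded POPS-normal respiratory rate positive, giving 0% specificity in that group. This follows from the SAP's own tables, taking the POPS score-0 ranges as normal and reading footnote c) literally. By respiratory rate the effect touches only the value 25 at ages 5-12 and none of the normal range at 13-16.

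The effect on overall child specificity cannot be fixed from the SAP. The illustrative 0.15 to 0.81 shows how far it depends on the age mix, the recording of respiratory rate and the six-item specificity. No figure for AUROC is supported.

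The child bands in 6.3 are a secondary matter: they misorder young children in a descriptive table and might carry into a child score.

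**What to change.** In footnote c), state that the version with NEWS2-based criterion G is calculated in adults only, and that in children the six-item version alone is reported. Note this in 6.2 and in the summary table in 8.9. The cost is one or two sentences and a condition in the scoring code; the G version is lost in children. Defining G from POPS or COAST instead is not advised, since it would build one comparator tool into another.

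For the child column in 6.3, reconcile the respiratory-rate and pulse bands, including where missing values go, with the age-specific ranges used elsewhere in the SAP (8.4 criterion B, 8.6.1, 8.7, 8.8), or use age-standardised values in the child tables and any child score. The POPS bands cannot be copied unchanged because some overlap as printed, for example respiratory rate 41-50 and 50+ at age 0-1. This costs SAP wording and recoding only; no new data are needed.
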